1.1.1. Primary Estimand

The primary clinical question of interest is: What is the difference in maximum reduction of HBsAg from baseline CCI in GSK3965193 vs. placebo in participants living with chronic hepatitis B infection, prior to prohibited medication use or temporary/permanent discontinuation of treatment?

Attributes of Estimand:

Variable/Endpoint	Treatment	Population	Population Summary
Maximum reduction of serum HBsAg levels from baseline CCI CCI CCI CCI	GSK3965193 and Placebo	PLWCHB treated on stable nucleos(t)ide analog (NA) therapy	Mean of maximum reduction in change from baseline over all patients in GSK3965193 and Placebo. Treatment difference (GSK3965193 – Placebo).

Intercurrent Event			Strategy	
Intercurrent Event	Details on the Intercurrent Event	Decision on the usage of data	Strategy	Rationale
Temporary or permanent discontinuation of dosing	Temporary or permanent discontinuation of IP dose include any of the following occurrences: 
 Missing 2 or more consecutive doses Permanent discontinuation from treatment Permanent discontinuation from study 	Data from Day 1 (post randomization) until start of temporary discontinuation or permanent discontinuation.	While on-treatment	Data will only be used until the start of temporary discontinuation or date of permanent discontinuation. This is to capture that the participant could not tolerate the study treatment as planned.

CCI

CCI

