- Compute the change in log10 HBsAg values from baseline for each post-baseline visit as: Log10 HBsAg at post baseline - Log10 HBsAg at baseline
- Maximum reduction in log10 HBsAg value is the minimum value of the calculated change from baseline at any post-baseline visit within the specified timeframe (CCI)

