4.1.2. Bayesian Methodology

The main statistical analyses will be carried out using a Bayesian framework.

Prior distributions are specified for each analysis. Posterior mean and 95% credible intervals (CrIs) along with the posterior probabilities of crossing pre-specified values of interest will be displayed, unless otherwise stated.

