4.2.2.4. Pharmacodynamic (HBsAg)

Unless otherwise specified, all PD analysis will be reported using PD analysis set.

CCI

CCI

CCI

CCI

CCI

.Following summaries will be provided -

- Summary of Change from Baseline in HBsAg by Visit and Treatment
- Summary of Time to Maximum Reduction in HBsAg

To estimate the mean of maximum reduction of serum HBsAg levels from baseline CCI, a Bayesian approach will be used. This approach will use Gumbel distribution $F(x, \alpha, \beta)$ as the likelihood function for the maximum \log_{10} HBsAg reduction.

For each participant, a non-informative prior will be used with α and β is assumed to be known. The posterior distribution for α will be derived and the posterior probabilities $P(\text{mean of maximum } \log_{10} \text{ HBsAg reduction} \geq \text{cutoff} \mid \text{data})$ will be obtained from the posterior distribution.

CCI

CCI

CCI

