4.2.3. Sensitivity analyses

Not Applicable

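### Part 3 primary HBsAg analysis: with the Gumbel scale β fixed, the width of each credible interval ignores the data, and each arm's mean is biased unless the assumed β is right

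*SAP*

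**What the plan says.** SAP 4.2.2.4 sets out the primary pharmacodynamic analysis of Part 3: "This approach will use Gumbel distribution" with parameters α and β as the likelihood for maximum log10 HBsAg reduction. On priors it says "For each participant, a non-informative prior will be used with" α, while β "is assumed to be known. The posterior distribution for" α is derived. The probability that the mean reduction reaches a cutoff is read from that posterior.

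SAP 4.1.2 names the reported results: "Posterior mean and 95% credible intervals (CrIs) along with the posterior probabilities of crossing pre-specified values of interest will be displayed". SAP 1.1.1 gives the target as "Mean of maximum reduction in change from baseline over all patients in GSK3965193 and Placebo", together with "Treatment difference (GSK3965193 – Placebo". On sensitivity analyses of the primary endpoints, SAP 4.2.3 says "Not Applicable".

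Text is blacked out directly after the model description in SAP 4.2.2.4 and at the matching place in protocol 9.4.2 (Part 3). The value of β, its source, whether it differs by arm, the cutoffs and the arm sizes may all stand there. None of them is treated here as missing from the plan.

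**The concern.** In a Gumbel model the mean is α + 0.5772β, so β sets both the spread and part of the mean. Fixing it asserts that the between-participant spread is known before the data are seen. Protocol 2.2 reports that no participant with chronic hepatitis B had received GSK3965193 at the October 2023 data cut-off, so Part 3 is the first look at this response in patients. There is also no evident reason why a treated arm and a placebo arm should share one spread.

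At stake are the posterior mean, the 95% credible interval and the crossing probabilities for a primary endpoint. If they depend on an assumed β and no other β is tried, a reader cannot tell how much of the result comes from the data.

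**Working it through.** **Inputs.** The likelihood, the prior and the known β come from SAP 4.2.2.4. The plan shows no figure that can be reproduced, because β, the cutoffs and the arm sizes are redacted. SAP 1.1.3 equates more than 20% of participants with 4 or more. If 4 is the smallest such count, then 4/N > 0.20 gives N < 20 and 3/N ≤ 0.20 gives N ≥ 15, so total N is 15 to 19. Allocation is not visible, so n = 5 to 15 per arm is an assumed range.

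Let x be the reduction taken as a positive number, as a cutoff of the form ≥ implies, and use the standard Gumbel form for maxima. SAP 4.1.1 writes that "Maximum reduction in log10 HBsAg value is the minimum value of the calculated change from baseline", which is a negative number when HBsAg falls. If the same form were applied to that signed value, the directions below would reverse. The widths would not change.

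**Step 1: posterior.** With β fixed at β0, a flat prior on α and S = Σexp(-x/β0), exp(α/β0) given the data is Gamma(n, rate S). The 95% limits for the mean are β0(ln q − ln S) + 0.5772β0, where q is the 0.025 or 0.975 quantile of Gamma(n, 1).

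**Step 2: width.** S cancels, so width = β0(ln q0.975 − ln q0.025). For n = 8 the quantiles are 3.454 and 14.423, and width = (2.669 − 1.239)β0 = 1.43β0. It is 1.84β0 at n = 5, 1.27β0 at n = 10 and 1.03β0 at n = 15, whatever the data.

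Example with n = 8 and β0 = 0.2 (assumed). The values 0.1, 0.2, …, 0.8 have mean 0.45 and SD 0.245. Tripling each deviation from 0.45 keeps the mean and raises the SD to 0.735.

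| Data | S | 95% interval | Width |
|---|---|---|---|
| SD 0.245 | 1.513 | 0.280 to 0.566 | 0.286 |
| SD 0.735 | 25.85 | -0.287 to -0.001 | 0.286 |

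The width does not change. The centre does, and the second interval excludes its own sample mean.

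**Step 3: bias.** Let r = true β / β0. The large-sample bias of the mean is β0[0.5772(1 − r) − lnΓ(1 + r)], which is zero only at r = 1.

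- r = 1.5: 0.5772(−0.5) − ln 1.3293 = −0.2886 − 0.2847 = −0.57β0.
- r = 0.5: 0.5772(0.5) − ln 0.8862 = 0.2886 + 0.1208 = +0.41β0.

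**Step 4: small samples.** Simulated from a true Gumbel, 200,000 trials per cell; bias is in units of β0:

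| n per arm | Coverage, r = 1 | Coverage, r = 1.5 | Bias, r = 1.5 | Coverage, r = 0.5 | Bias, r = 0.5 |
|---|---|---|---|---|---|
| 5 | 0.95 | 0.66 | -0.44 | 0.99 | +0.34 |
| 8 | 0.95 | 0.58 | -0.49 | 0.98 | +0.36 |
| 10 | 0.95 | 0.53 | -0.51 | 0.96 | +0.37 |
| 15 | 0.95 | 0.43 | -0.53 | 0.88 | +0.39 |

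**Step 5: treatment difference.** One β0 is used for both arms, and bias is in units of the active arm's true β.

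- Arms of 8 and 8 with the same true β: within 0.004.
- Arms of 12 and 4 with the same true β: −0.12 when β0 is half the true value, +0.12 when it is double.
- Placebo true β half the active one: −0.06 to −0.57 over the allocations tried, with β0 from half to twice the active arm's true β.

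**Step 6: β estimated.** With a prior proportional to 1/β, coverage was 0.951, 0.959, 0.955 and 0.948 at n = 5, 8, 10 and 15. Median width was 2.84, 2.02, 1.75 and 1.37 times the true β, and it followed the sample SD (correlation 0.83 to 0.94).

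**The case against.** The strongest reply is that redaction hides what would settle the matter. The blacked-out lines may give a well-founded β, a separate β for each arm, or a plug-in from the trial's own data. With a plug-in the width would follow the spread, and the remaining fault would be that uncertainty in β is omitted. That is fair, and it is why no size or direction can be claimed for this trial. The visible text nevertheless treats β as known and derives a posterior for α only.

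A reader might infer four stronger claims that do not hold.

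- That the observed scatter plays no part. It enters the centre of the interval through S, and that is where the bias comes from. Only the width is free of the data.
- That the intervals are always too narrow. If the assumed β is too large, coverage stays near or above 95% in the smaller arms and falls to 0.88 at n = 15. The main harm is then an overstated mean.
- That the treatment difference must be wrong. With arms of equal size and one true β, the bias largely cancels there, though it remains in each arm's mean and in P(mean ≥ cutoff).
- That the decision on Part 4 rests on this posterior. Protocol 4.2.4 makes Part 4 contingent on Part 3 safety and efficacy data without naming this analysis, and the interim text is redacted.

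The SAP also reports change in HBsAg by visit with SDs and confidence intervals, individual plots and responder proportions, and it tests no hypothesis. These soften the consequence. They do not replace the primary summary.

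**Conclusion.** The concern holds for each arm's mean and its crossing probability. As the visible SAP reads, interval width is a function of n and the assumed β alone, the mean is biased unless that β is right, and no other β is tried. Over the assumed n of 5 to 15 per arm, coverage is about 0.66 to 0.43 when the true β is 1.5 times the assumed one, against a nominal 0.95. When the true β is half the assumed one, coverage is about 0.99 to 0.88, with a large-sample overstatement of 0.41β0.

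The form of the defect is certain from the text. Its size and direction here are not, because they rest on assumed ratios, assumed arm sizes and data that truly follow a Gumbel distribution. In the difference between arms it matters chiefly if the arms differ in size or in true scale.

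**What to change.** In SAP 4.2.2.4, give β a weakly informative prior and let it differ by arm. If the placebo arm is very small, use partial pooling or state the prior explicitly, since the prior will then carry weight. Report the joint posterior of α + 0.5772β for each arm and of the GSK3965193 minus placebo difference, which is the summary the estimand asks for. In SAP 4.2.3, replace the current entry with the fixed-β fit over a prespecified range of β.

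The cost is a few lines of code and wider intervals. Against a correctly fixed β, the median width rises from 1.84 to 2.84 times β at n = 5 (54%) and from 1.03 to 1.37 at n = 15 (33%). No new data are needed.

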4.2.3. Sensitivity analyses

Not Applicable

4.3. Secondary Endpoint(s) Analyses

The secondary objectives of Part 3 are following –

- To evaluate the PK characteristics of repeat doses of GSK3965193 in PLWCHB
- To evaluate PD effect of GSK3965193 monotherapy in PLWCHB
- To assess the safety and tolerability of bepirovirsen monotherapy in PLWCHB who have completed GSK3965193/placebo monotherapy.

4.3.1. Key secondary endpoint(s)

4.3.1.1. Definition of endpoints

The following endpoints will be assessed.

- AUC(0-tau), Cmax, Tmax, and apparent terminal half-life (T1/2) will be calculated as data permits.
- $\geq 0.5x$ log IU/mL reduction of serum HBsAg levels from baseline anytime during the study (on-treatment and post-treatment)
- Optional Bepirovirsen Extension Only: Incidence of AEs, SAEs, withdrawals due to AEs. Incidence of clinically significant laboratory parameters (haematology, clinical chemistry, urinalysis) and vital signs.

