### Part 2B

Part 2B assessed CCI of GSK3965193 under CCI. Participants received CCI GSK3965193 (open label) CCI. These two periods were CCI GSK3965193 tablets CCI

Participants were enrolled for approximately CCI

## Part 3

Part 3 will assess repeat doses of GSK3965193 in CCI of PLWCHB on stable NA therapy. CCI receive either GSK3965193 or placebo as CCI. The dose of GSK3965193 for Part 3 CCI

After GSK3965193 or placebo dosing and 2 weeks of washout, participants in this cohort with screening HBsAg levels [REDACTED] will be given the option to continue in the study and [REDACTED]

[REDACTED] bepirovirsen treatment.  
Participants can enroll in Part 3 even if they choose not to receive bepirovirsen.

Participants who do not participate in the optional bepirovirsen treatment will be enrolled for approximately [REDACTED]

Participants who opt to continue with bepirovirsen treatment will be enrolled for approximately [REDACTED]

#### Part 4

Part 4 will assess repeat doses of GSK3965193 dosed concurrently with bepirovirsen in a [REDACTED] of PLWCHB on stable NA therapy [REDACTED] participants will be randomized in a [REDACTED] to receive either GSK3965193 or placebo [REDACTED]. The dose of GSK3965193 [REDACTED]

Bepirovirsen dosing will continue [REDACTED] after GSK3965193 or placebo dosing completes.

Participants will be enrolled for approximately [REDACTED]

[REDACTED], and approximately [REDACTED]

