Primary Objective 2: To evaluate PD effect of GSK3965193 monotherapy in PLWCHB (Part 3)  First Main Estimand	
 
Maximum reduction of serum HBsAg levels from baseline CCI [REDACTED]
 
	
 
Hypothetical strategy, discontinuation of, interruption in, and non-adherence to GSK3965193 related to or not related to any wide disruptive events will be handled assuming they had not happened (hypothetical strategy).
 
	
 
Mean averaged over all PLWCHB in each treatment group
 

Primary Objective 3: To evaluate efficacy of GSK3965193 in combination with bepirovirsen (Part 4)  Second Main Estimand	
 
Achieving complete response (undetectable serum HBV DNA and HBsAg for 6 months after the planned end of treatment of bepirovirsen)
 
	
 
Intercurrent event of discontinuation of, interruption in, and non-adherence to GSK3965193 not related to any wide disruptive events and for change in the background NA therapy will be ignored (treatment policy strategy)
 
Wide disruptive events (such as COVID-19 pandemic) leading to discontinuation of, interruption in, and non-adherence to bepirovirsen and GSK3965193 will be handled assuming they had not
 
	
 
Proportion of PLWCHB
 

Estimand Category	Estimand (Part 3 and Part 4)		
	Variable/Endpoint	Intercurrent Event Strategy	Population Level Summary Measure
		happened (hypothetical strategy).	
Secondary Objective 1: To evaluate pharmacodynamic (PD) effect of GSK3965193 monotherapy in PLWCHB (Part 3) Third Main Estimand	
 
• <math>\geq 0.5 \times \log</math> IU/mL reduction of serum HBsAg levels from baseline any time during the study (on-treatment and post-treatment)
 
	
 
• Same as Primary Objective 2 for Part 3
 
	
 
• Proportion of PLWCHB
 

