#### 9.4.3. Secondary Endpoint(s)

The first secondary objective is to evaluate the PK characteristics of repeat doses of GSK3965193 in PLWCHB of Part 3. The description of pharmacokinetic analysis is in Section 9.4.7.

Part 3:

A secondary objective for Part 3 is to evaluate the PD effect of GSK3965193 monotherapy in PLWCHB. The PD analyses will be based on the ITT population.

The third main estimand supporting this secondary objective for Part 3 the same as the first main estimand supporting the primary PD objective for Part 3, except the following:

- Variable:
  - Categorical:  $\geq 0.5 \times \log_{10}$  IU/mL reduction of serum HBsAg levels from baseline loss of HBsAg any time during the study
- Population-level Summary:
  - Categorical: Proportion of PLWCHB

CCI

Part 4:

A secondary objective for Part 4 is to evaluate the PD effect of GSK3965193 in combination with bepirovirsen in PLWCHB.

The fourth main estimand supporting this secondary objective for Part 4 is defined the same as the second main estimand supporting the primary efficacy objective for Part 4, except that the variable is PLWCHB experiencing HBsAg loss anytime during the study.

CCI

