Table 17	Study Period Definition.....	39
Table 18	Definitions of Assessment Windows for Early discontinuation	40

LIST OF FIGURES

	PAGE
Figure 1	
Participants receiving GSK3965193 or Placebo monotherapy only.	14
Figure 2	
Participants with HBsAg levels ≤ 3000 IU/mL at screen who choose to receive optional open label bepirovirsen treatment.	14

VERSION HISTORY

SAP Version	Approval Date	Protocol Version (Date) on which SAP is Based	Change	Rationale
SAP	30 May 2024	Protocol Amendment Version 8.0 (26 March 2024)	Original Version	Statistical Analysis Plan for Part 3
SAP Amendment 1	26 May 2025	Protocol Amendment Version 10.0 (10 March 2025)	Section 1.: Details on Intercurrent event have been updated	Clarification
			Section 3: Additional text has been added for Randomized, PK and PD analysis set in defining the population and how the data will be reported	Clarification
			Section 4. Added the imputation value to be used for the biomarkers value if they turn out to be LLOQ or TND. Methodology has been added for the derivation of log10 Change from Baseline for HBsAg and Maximum reduction of log10 HBsAg	Clarification

SAP Version	Approval Date	Protocol Version (Date) on which SAP is Based	Change	Rationale
			Removed CCI [REDACTED] CCI [REDACTED] CCI [REDACTED] from Parameters list in the Table 4 as they are in the collect and hold strategy list Methodology to summarize laboratory, vital signs and ECG Data has been updated Additional summaries related to TEAEs are added	
			Section 6. Updated the information on PCI criteria and Assessment window	Clarification
SAP Amendment 2	01 August 2025	Protocol Amendment Version 10.0 (10 March 2025)	4.4.2.4 Additional details on the analysis to understand target engagement added	Detailed specification
SAP Amendment 3	07 Apr 2026	Protocol Amendment Version 10.0 (10 March 2025)	Section 4.3.1.2.3: Updated the derivation of TEAEs for Bepi period	Clarification and Detailed specification

SAP Version	Approval Date	Protocol Version (Date) on which SAP is Based	Change	Rationale
			Section 4.4.3: Reduced Number of PK parameters which will be assessed for Bepi period	

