4.3.1.2.2. Pharmacodynamic Analysis

HBsAg will be collected CCI
GSK3965193 treatment period. Again, HBsAg will be collected from CCI
CCI

Individual line plot will be provided for change from baseline for HBsAg levels
GSK3965193 and Placebo CCI

Following summaries will be provided -

- Proportion of PLWCHB who achieved HBsAg $\geq 0.5 \log_{10}$ IU/mL decline and/or <LLOQ in HBsAg at any Visit during the Treatment

CCI

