4.5.1. Extent of Exposure

Extent of exposure to study intervention will be summarized. The number of days of exposure to study treatment (GSK3965193/Placebo) will be calculated based on the formula given below:

Duration of Exposure (in Days) = (Treatment Stop Date – Treatment Start Date) + 1

Participants who were randomized but did not report a treatment start date will be categorized as having zero days of exposure. The cumulative dose will be based on the formula:

Cumulative Dose = Sum of (Number of Exposure Days x Total Daily Dose)

Optional Bepirovirsen arm will be using 300mg Bepirovirsen Subcutaneous (SC) weekly dose until week 24 weekly, plus additional 300mg loading doses in weeks 1 and 2.

Number of participants with < 6 weeks, <=12 weeks, <=24 weeks exposure and > 24 weeks exposure will be presented, and overall duration will be summarized.

Number of days of exposure to study drug will be calculated based on the formula below:
Duration of Exposure in Days = Last injection date – First injection date + 1

The cumulative dose will be based on the formula below:

Cumulative Dose = Number of Injections of 300mg x 300mg + Number of Loading doses x 300mg.

In case of temporary treatment hold for 1 or more than 1 day, for both GSK3965193 and for optional bepirovirsen arm, the following formula will be used for calculation of “Duration of Exposure”.

Duration of Actual Exposure (in Days) = (Treatment Stop Date – Treatment Start Date + 1) – Number of days treatment on hold.

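### The Part 3 secondary responder endpoint has conflicting time windows, and no visible rule keeps HBsAg falls on optional bepirovirsen out of the widest one

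*SAP*

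**What the plan says.** The objective is the pharmacodynamic effect of GSK3965193 monotherapy. The responder endpoint supporting it is described in several places.

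- **SAP 1.1 and 4.3.1.1:** a 0.5 log or greater "reduction of serum HBsAg levels from baseline anytime during the study (on-treatment and post-treatment". The protocol synopsis and Section 3 match, and Protocol Table 2 has "reduction of serum HBsAg levels from baseline any time during the study (on-treatment and post-treatment".
- **Protocol 9.4.3:** the same study-long window, with a garbled variable: "reduction of serum HBsAg levels from baseline loss of HBsAg any time during the study".
- **SAP 4.3.1.2.2 (planned summary):** the proportion with a 0.5 log decline and/or "<LLOQ in HBsAg at any Visit during the Treatment".
- **SAP 1.1.2 (secondary estimand):** GSK3965193 against placebo, before prohibited medication or discontinuation, with intercurrent events handled as for the primary endpoint, that is, while on treatment. The time window is blacked out.

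Optional bepirovirsen belongs to Part 3. The synopsis says "After GSK3965193 or placebo dosing and 2 weeks of washout, participants in this cohort with screening HBsAg levels" at or below a blacked-out limit "will be given the option to continue in the study and" receive it. The SAP's Figure 2 title shows the limit: "Participants with HBsAg levels ≤ 3000 IU/mL at screen who choose to receive optional open label bepirovirsen treatment". SAP 4.5.1 gives its length: "Optional Bepirovirsen arm will be using 300mg Bepirovirsen Subcutaneous (SC) weekly dose until week 24".

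**The concern.** The visible definitions of one endpoint do not agree. One includes a post-treatment period of unstated length; another stops with treatment. Two programmers working from SAP 4.3.1.1 and 4.3.1.2.2 could produce different responder tables, and choosing between them with results in hand would be post hoc.

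The wider window has a further weakness. Participants who decline bepirovirsen are followed for two weeks off treatment; those who accept stay in the study through a 24-week course and its follow-up. A window running to the end of the study would therefore differ in length between participants according to a choice made after randomisation. For those who accept, it would include exposure to a second drug that lowers HBsAg. Bepirovirsen is offered to both randomised arms, so counting those falls would raise both rates and tend to pull them together. The result would no longer describe GSK3965193 monotherapy.

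**Working it through.** **1. The windows compared.** Take two participants with no 0.5 log fall while on GSK3965193 or placebo.

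- *First reaches a 0.5 log fall in the washout:* responder under SAP 4.3.1.1; not under SAP 4.3.1.2.2.
- *First reaches it on bepirovirsen:* responder under SAP 4.3.1.1 read literally; not under SAP 4.3.1.2.2 if treatment there means GSK3965193 or placebo. That section does not say which treatment it means, in a part that has two.

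The below-LLOQ addition matters less. Entry requires HBsAg above 100 IU/mL (Protocol 5.1.3) and the LLOQ is 0.05 IU/mL (SAP Table 1). From 100 IU/mL, reaching the LLOQ is a fall of log10(100/0.05) = 3.3, so under *or* it adds nobody with a baseline near the entry level or higher. Under *and* it would be far stricter, so the wording should still be settled.

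**2. Does any visible rule close the wide window before bepirovirsen?**

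- *Discontinuation (SAP 1.1.1):* defined by missed consecutive doses or by permanent discontinuation of treatment or study. Completing GSK3965193/placebo and moving on is none of these.
- *Prohibited medication (Protocol 6.8.2):* does not list the bepirovirsen that the protocol itself supplies.
- *Separate OBE set (SAP 3 and 4.3.1.2):* an analysis set selects people, not dates. OBE participants are not removed from the PD set, and the PD set has no date limit.
- *Study periods (SAP Table 17):* supply a usable boundary at the bepirovirsen start, but nothing visible ties the responder endpoint to it.

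By contrast, SAP 4.2.2.1 closes the GSK3965193/placebo adverse-event window at last dose plus 7 days. No equivalent for HBsAg is visible.

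**3. Size if bepirovirsen-period falls were counted.** The visible text gives no sample size, uptake or expected rate for this endpoint, so there is no planned figure to reproduce. Inputs:

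- q, the probability that a participant who has not yet responded reaches 0.5 log on bepirovirsen. Protocol 2.2 cites 7/12 = 58.3% by Day 29, in treatment-naive participants. Illustrative only.
- f, the share of each arm taking bepirovirsen. Not given; 25%, 50% and 75% are assumed.
- p, the true response rate before bepirovirsen. Assumed 0% on placebo and 50% on GSK3965193.

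With f and q equal in both arms and independent of the first response:

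observed rate = p + (1 − p)×f×q

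observed difference = (p1 − p0)×(1 − f×q)

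| f | f×q | Placebo | GSK3965193 | Difference (points) | Share kept |
|---|---|---|---|---|---|
| 0% | 0 | 0% | 50% | 50 | 100% |
| 25% | 0.146 | 14.6% | 57.3% | 42.7 | 85% |
| 50% | 0.292 | 29.2% | 64.6% | 35.4 | 71% |
| 75% | 0.438 | 43.8% | 71.9% | 28.1 | 56% |

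The share kept does not depend on the assumed p. At q = 80% it would be 1 − 0.25×0.8 = 80%, 1 − 0.5×0.8 = 60% and 1 − 0.75×0.8 = 40%. Closing the window before bepirovirsen sets f×q to zero, the first row.

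**The case against.** The strongest reply is that the governing definition cannot be seen. SAP Table 12 says the secondary estimand was re-defined and points to SAP 1.1.2, where a block is blacked out just where a time window would stand. The visible intercurrent-event table is also incomplete: the clinical question names prohibited medication, yet no visible row handles it. The absence of bepirovirsen from that table therefore proves nothing.

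Much of the legible text also separates the two drugs. The handling is while on-treatment, the planned summary is limited to treatment, bepirovirsen pharmacodynamics go to the OBE set, HBsAg has its own bepirovirsen baseline (SAP Table 4), and the periods are distinct in SAP Table 17. On this reading, post-treatment means only the two-week washout.

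This stands against the stronger inference that a reader might draw, namely that the plan does credit bepirovirsen responses to GSK3965193 and placebo. The documents do not support that as fact. It is also fair that 7/12 comes from treatment-naive participants, whereas Part 3 requires stable NA therapy. Uptake is unknown and restricted by screening HBsAg, so the figures cannot be called a lower bound or an estimate for Part 3.

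It does not remove the conflict. If the hidden window closes before bepirovirsen, SAP 1.1 and 4.3.1.1 contradict it; if it does not, the contamination is real. Either way, SAP 4.3.1.1 and 4.3.1.2.2 disagree in legible text on whether post-treatment falls count.

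**Conclusion.** Wrong as written: the endpoint rule conflicts with itself, and the widest visible version, read literally, would count falls on bepirovirsen in both arms. Whether they would be counted in practice cannot be settled from the visible text.

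If they were, the arm difference would keep 85%, 71% or 56% of its size at uptake of 25%, 50% or 75%. That rests on q = 58% from another population, assumed uptake, and equal uptake and response in both arms. If these differed by arm, the simple multiplier would not apply and the direction of the bias could not be assumed.

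Severity is moderate. The endpoint is secondary, no hypothesis is formally tested, so no type I error is at stake, and the primary HBsAg endpoint has its own (blacked-out) timeframe and is not shown to be affected. The cost is an ambiguous programming instruction and a possibly diluted estimate.

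**What to change.** Use one window in SAP 1.1, 1.1.2, 4.3.1.1 and 4.3.1.2.2, and in the protocol synopsis, Section 3, Table 2 and 9.4.3. It should run from the first GSK3965193/placebo dose to the last HBsAg sample before the first bepirovirsen dose, and no later than the two-week washout visit (Protocol 7.1 refers to a Day 43 visit as the point before bepirovirsen). It should be the same for participants who do and do not opt in.

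State that the washout counts, or delete the post-treatment wording. Reconcile this with the while on-treatment handling, name the treatment meant in SAP 4.3.1.2.2, and settle the and/or before the LLOQ criterion and the stray loss-of-HBsAg wording in Protocol 9.4.3. Report falls during bepirovirsen only in the OBE set, from the bepirovirsen baseline.

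The cost is wording in two documents and one programming cut-off. No visit, sample or treatment changes. It should be settled before anyone chooses between windows with unblinded HBsAg results in hand.
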